#### **4.16 Clinical Monitoring Procedures**

Clinical studies coordinated by The University of Michigan Rogel Cancer Center must be conducted in accordance with the ethical principles that are consistent with Good Clinical Practices (GCP) and in compliance with other applicable regulatory requirements.

Prior to subject recruitment, a participating site will undergo site initiation meeting to be conducted by the Study PI/Delegate. This will be done as an actual site visit; teleconference, videoconference, or web-based meeting. The site's principal investigator and study staff should make every effort in attending the

site initiation meeting. Study-related questions or issues identified during the site initiation meeting will be followed-up by the appropriate personnel until they have been answered and resolved. Monitoring of this study will include centralized surveillance of study specific data at a defined cadence.

Participating sites will also undergo a site close-out upon completion, termination, or cancellation of a study to ensure fulfillment of study obligations during the conduct of the study, and that the site Investigator is aware of his/her ongoing responsibilities. In general, the site close-out can occur without a site visit.

## **5.0 STATISTICAL CONSIDERATIONS**

### **5.1 Study Design**

This study will use a two-arm randomized design. Each caregiver-patient dyad will be randomized to an active “treatment” arm (mobile platform + Roadmap 2.0) or to a control arm (Mobile platform + usual care). The random allocation of participants to the treatment arm or control arm establishes the basis for testing the statistical significance or difference between the groups in the measured outcome (caregiver health-related quality of life, assessed by the PROMIS Global Health scale). Caregiver age, gender, and other prognostic baseline characteristics that could potentially confound an observed association, including those that are unknown or unmeasured, will be distributed equally, except through chance alone, through random assignment. Thus, this design is well-suited to our goal of assessing the efficacy of a mobile health intervention, Roadmap 2.0, on caregivers.

### **5.2 Accrual**

It is estimated that 5 years will be necessary to enroll the targeted sample size. Accrual will be reported by race, ethnicity, gender, and age.

### **5.3 Study Duration**

Participants will be followed on intervention for 120-days post-transplant for primary, secondary, and exploratory endpoints. Subjects will remain in follow-up for 1-year post-HCT. The study team will have access to the electronic medical records for 1-year post-HCT.

### **5.4 Randomization**

Blocked randomization will be used to limit bias and achieve an equal distribution of participants to the treatment and control arms. This approach will recruit participants in small blocks to ensure that half of the participants within each block will be allocated to the treatment and the other half to the control. The size of the blocks will be permuted to limit selection bias, and within each block, the

order of patients will be random. Randomization will be stratified by type of transplant (adult allo, adult auto, pediatric), so that three separate randomization lists will be created. The study statistician, [name] (Co-I), will create the randomization lists before the study begins enrollment using the statistical package R. Assignments will be allocated in list order, and an assignment will not be reused with future patients if a patient later declines to participate after being randomized. Adequate training will be given to the Project Manager and Research Coordinator, including enrollment of participants, allocation of treatment arm, and training the participants.

## **5.5 Blinding**

Study arm assignments cannot be blinded to the investigators nor the subjects, because it will be known whether participants have the positive activity components of Roadmap 2.0 on their mobile device or not (due to technical purposes). Treatment assignments will not be blinded to the statistician/data scientists ([name], Co-I, and his research staff) or other Study Team members who will be ascertaining and adjudicating the outcomes ([name], Co-I, and her research staff). In addition, Research Assistants who collect the outcomes data (e.g., participant reported outcome measures, interviews) will be different from the Research Coordinator who will provide study training and ensuring weekly adherence to the study protocol (e.g., fidelity).

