## 2.5 Intervention Plan

### 2.5.1 How will the intervention work?

Participants (caregiver-patient dyads) who are consented, enrolled, and randomized will be scheduled for a one-hour training session with the Research Coordinator(s) prior to or during admission to undergo the HCT. Based on our experience, these training sessions will be coordinated with other clinic appointments at the hospital in efforts to minimize burden on the caregiver and patient or remotely via institutionally approved virtual meeting platform. Once the intervention has begun, the Research Coordinator(s) will meet with the participants (caregiver-patient dyad) weekly to review any questions or concerns, to perform data download (wearable sensor device), and to ensure adherence to the protocol. HCT patients are typically inpatient for approximately four weeks. During this period, the Research Coordinator(s) will be available by pager and will schedule weekly visits with the participants or virtual visits. Once discharged, HCT patients return to clinic on a weekly visit in the ambulatory care setting. The Research Coordinator will meet with participants during those routine appointments. Roadmap 2.0 software will be maintained in collaboration with Arbormoon Software, Inc.

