## **5.10 Analysis Populations and General Analysis Guidelines**

### **5.10.1 Primary Analysis Population**

All participants enrolled, consented, and completing at least the baseline outcome measures will be included in the primary analysis population. Analyses for the primary and secondary endpoints will use the primary analysis population: Caregivers of adult patients [age  $\geq 18$  years] will be analyzed separately from caregivers of pediatric patients [age 5-17 years]). The primary analysis will occur once all patients have been followed for 120-days post-transplant, data adjudication completed, and data are locked.

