## **5.11 Analysis of Primary Endpoint**

Analysis will be an intent-to-treat analysis that includes all caregivers. Mean Global Health scores for each arm at day 120 will be compared using a two-sample *t*-test (or Wilcoxon Rank Sum test if non-normality is apparent) with a significance level of 0.05. Linear regression models will be performed to complement the results of the *t*-test and adjust for specific baseline caregiver characteristics (e.g., demographic, social, environmental) to increase the precision of our inference. We plan to do analyses separately for allo dyads, auto dyads, and pediatric dyads, although we have only powered the study for the analysis in the allo dyads. There is a possibility that patient characteristics will be unbalanced since our randomization scheme will be applied to caregivers. Thus, our models also will assess potential moderating or mediating effects, described below.

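### Section 5.5 leaves the analyst and the outcome adjudicators unblinded for a reason that does not prevent masked arm codes

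*Combined protocol and SAP*

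**What the plan says.** Section 5.5 first gives the reason for an open trial: "Study arm assignments cannot be blinded to the investigators nor the subjects, because it will be known whether participants have the positive activity components" on their device. The next sentence goes further: "Treatment assignments will not be blinded to the statistician/data scientists". It also names "other Study Team members who will be ascertaining and adjudicating the outcomes". It carries no reason of its own. The sentence after that opens with *In addition* and describes a safeguard: the Research Assistants who collect outcome data "will be different from the Research Coordinator who will provide study training" and who follows weekly adherence. It does not say that the assistants are masked.

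Section 5.11 makes a two-sample t-test at 0.05 the primary comparison, "or Wilcoxon Rank Sum test if non-normality is apparent", without a criterion for non-normality. Regressions are to complement it and to "adjust for specific baseline caregiver characteristics (e.g., demographic, social, environmental"; the covariates are given by example only. Section 5.10.1 places the primary analysis after follow-up, with "data adjudication completed, and data are locked". No section mentions masked arm codes, a blinded data review, or settling these choices before arm is known.

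**The concern.** What is on a caregiver's phone explains why caregivers, patients and the staff who train them cannot be masked. It does not explain why a data file must show arm identity to the person who analyses it or to those who adjudicate outcomes. Where a plan leaves decisions to be taken on the data, masking keeps those decisions from leaning towards one arm, even unintentionally. This plan leaves several such decisions open around a single primary test, and the trial is already exposed to reporting bias because caregivers who know their arm rate themselves. An open analysis and open adjudication add a further source of bias that could be avoided cheaply.

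**Working it through.** **1. Does the stated reason reach the people left unblinded?**

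| Role | Does device visibility prevent masking? |
|---|---|
| Caregiver, patient, training coordinator | Yes |
| Research Assistants collecting outcomes | Partly: the interview guide in Appendix D asks about the positive activities where applicable |
| Outcome adjudicators | No: their files can carry a code |
| Statistician/data scientists | No: the analysis file can carry a code |

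The statistician does have another route to the allocation. Sections 4.5 and 5.4 have the statistician create the randomization lists. Section 5.5 does not offer this as a reason, and dividing the tasks deals with it.

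**2. Which decisions are open when arm is known?**

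- Test: t-test or Wilcoxon, with no criterion (5.11).
- Covariates of the complementary regression: no fixed list (5.11).
- Analysis set: section 3.1 excludes caregivers whose patient relapses or dies before the endpoint, or who lack the day 120 scale; 5.10.1 takes everyone with baseline measures; 5.11 takes all caregivers by intention to treat. An example shows that these can differ. The survey window in 4.8 runs from day 120 − 30 = 90 to day 120 + 30 = 150. If a caregiver answers on day 95 and the patient relapses on day 110, there is a score that 5.11 would count and that 3.1, read against day 120, would not.

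**3. The plan's own figure.** Inputs from 5.7: effect size 0.5, two-sided alpha 0.05, power 0.80.

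- Normal approximation: n = 2(1.960 + 0.842)²/0.5² = 62.8, so 63 per arm.
- t-test: 63.8, so 64.
- Wilcoxon: 63.77 × π/3 = 66.8, so 67, which matches the stated 67.
- Power at 67 per arm: 0.819 (t-test), 0.800 (Wilcoxon, simulated).

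Masking changes none of these inputs.

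**4. How much room do the open choices leave?** Simulation under no effect, 67 per arm, keeping the smallest p-value:

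| Rule | Normal data | Skewed data (gamma, shape 2) |
|---|---|---|
| t-test fixed in advance | 0.047 | 0.050 |
| Wilcoxon fixed in advance | 0.049 | 0.050 |
| Better of the two | 0.058 | 0.065 |

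(10,000 runs; Monte Carlo SE about 0.002.)

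For the regression, the documents give neither the number nor the strength of the covariates. Both are assumed here: 1, 3 or 5 covariates, each with an effect of 0.2 or 0.4 residual SD per covariate SD, keeping the best of all subsets.

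| Covariates | Effect 0.2 | Effect 0.4 |
|---|---|---|
| 1 | 0.058 | 0.070 |
| 3 | 0.086 | 0.114 |
| 5 | 0.119 | 0.161 |

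(2,500 to 4,000 runs.) Allowing the Wilcoxon test as well moves the range to 0.067 to 0.165. The analysis-set choice was not simulated.

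**5. Is this an effect of unblinding?** No. Swapping the arm labels turns t into −t, U into n² − U, and the arm coefficient into its negative. Every two-sided p-value stays the same. An analyst who sees only codes A and B could pick the smallest p-value just as well. The figures in step 4 therefore measure missing pre-specification. Masking acts elsewhere: it removes knowledge of which arm a decision favours, which matters for adjudication and for who is counted.

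**The case against.** The best case for the plan is that staff have little influence on the primary endpoint. It is the caregiver's own report (5.6), collected through Qualtrics linked to the app (4.8), with item-level scoring described through the HealthMeasures Scoring Service (5.7). The main bias, self-rating by caregivers who know their arm, would remain after masking. That stands, and it limits the gain to analysis choices, evaluability decisions and outcomes that staff ascertain. It can also be said that the statistician and the outcomes lead are both co-investigators, so the word investigators in the first sentence of 5.5 could cover them. Even so, visibility on a device is no obstacle to a coded file. Finally, the sentence may simply be wrong: a safeguard introduced by *In addition* would follow more naturally from a statement that these people are blinded. That is a reason to ask the sponsor, not to pass over the text.

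A reader might infer more than the documents support:

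- That unblinding raises the type I error of the primary test to 10% or more. Step 5 rules out unblinding as the cause, and the larger figures concern regressions that only complement the primary test.
- That relapse dates are adjudicated by unblinded staff. No section says what is adjudicated. Section 3.1 gives a written rule, with censoring at the patient's last examination.
- That section 2.5.1 defeats the staff separation, because the coordinator meets dyads weekly "to perform data download (wearable sensor device), and to ensure adherence to the protocol". Sensor data are device-recorded and exploratory (3.2.12), and the examples given for the separation in 5.5 are participant-reported measures and interviews.
- That the confounders to be discovered under 5.13.4 bear on the primary test. They belong to the mediation models.

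**Conclusion.** The point holds in a limited form. As written, 5.5 makes open analysis and open adjudication the rule, gives no reason that fits, and no other section supplies masking. The bias this could cause cannot be sized from the documents. The open choice of primary test is worth at most about 0.8 to 1.5 percentage points of type I error (5.8% to 6.5% against 5%), assuming deliberate selection, 67 per arm, and normal or moderately skewed scores. The 5.8% to 16.1% range for adjusted models rests on assumed covariates and does not apply to the primary p-value. All these figures are upper bounds for unspecified choices, not predictions and not consequences of unblinding. The change is worth making because it is cheap and leaves the 67 per arm and the 80% power as they are.

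**What to change.** Ask the sponsor first whether the sentence in 5.5 was meant to say that these people are blinded. In either case, revise 5.5 to state:

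- Participants, investigators in contact with them and the training coordinator are unblinded.
- Outcome adjudicators, the analyst and, as far as interview content allows, the outcome-collecting Research Assistants work without arm identity until database lock.
- The primary test, the covariates and one analysis set (reconciling 3.1, 5.10.1 and 5.11) are fixed in writing, using pooled data with no arm variable, before any comparison between arms. Coded labels alone would not achieve this.
- Because the statistician generates the lists, the masked analysis is run by a member of the existing statistical staff without access to them.
- The code stays with the data manager/coordinator, who already holds the allocation under 4.5 and takes no part in analysis or adjudication.

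If the sponsor considers masking infeasible for any of these roles, 5.5 should say why.

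The cost is a recoded arm variable, a division of tasks within the statistical group, and withholding app-usage, MARS and interview fields, which can reveal arm, until lock. Sample size, endpoints, visits and care are unchanged.

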## **5.6 Primary Endpoint**

The primary endpoint of this trial is the self-report outcome measure of caregiver HRQOL. The primary objective of this clinical trial is to test Roadmap 2.0/Positive Activities in caregiver-patient dyads undergoing HCT and determining the statistical significance or difference between the treatment arm and control arm in caregiver HRQOL. We will use a hypothesis testing framework to assess the potential efficacy of a mobile health intervention (Roadmap 2.0) to improve caregiver HRQOL.

## **5.7 Sample Size Considerations**

The power calculation was completed by [name] using simulations in the statistical package R. Our primary endpoint (i.e., caregiver health-related quality of life from the PROMIS® Global Health scale) is focused solely on this outcome in caregivers, while our secondary endpoints are based on outcomes for both caregivers and patients. Given this, we determined our sample size based solely on caregivers. The age- and sex-adjusted norm for the Global Health scale is 50 points, with a standard deviation of 10 points. These statistics have been shown to be generalizable to the allogeneic BMT population. Our study will have power of 0.80, assuming a two-sided Type I error rate of 0.05, to detect an effect size of 0.5 between the intervention and control arms if 67 caregivers are enrolled in each arm. A mean difference of one-half a standard deviation is biologically meaningful

and is considered a medium effect size for clinical trials. We will accrue a total of 83 caregivers in each arm to account for dropout, assuming a 5% failure to undergo BMT, 8% death before day 120, and 10% missing day 120 PRO from participants. These percentages are inflated but based on adjustments of published BMT data.

Because our main goal is to assess the primary objective in adult allo dyads, we plan accrue approximately 260 dyads with adult patients, as that is the expected number of total adult dyads needed to enroll at least 166 allo dyads. We also plan to enroll approximately 40 dyads with pediatric patients in the time it takes to enroll the 260 adult dyads.

PROMIS® measures use Item Response Theory (IRT), a family of statistical models that link individual questions to a presumed underlying trait or concept of global health represented by all items in the scale. PROMIS® instruments are scored using item-level calibrations. The most accurate way to score a PROMIS® instrument is to use the HealthMeasures Scoring Service, which our Study Team has experience with ([name], Co-I and [name], Co-I). This method of scoring uses “response pattern scoring,” which uses responses to each item for each participant. Response pattern scoring is especially useful when there is missing data (i.e., a respondent skipped an item), or different groups of participants responded to different items).

There are four key features of the score for PROMIS® Global Health:

1. Reliability: The degree to which a measure is free of error. It can be estimated by the internal consistency of the responses to the measure, or by correlating total scores on the measure from two time points when there has been no true change in what is being measured (for z-scores, reliability =  $1 - SE^2$ ).
2. Precision: The consistency of the estimated score (reciprocal of error variance).
3. Information: The precision of an item or multiple items at different levels of the underlying continuum (for z-scores, information =  $1/SE^2$ ).
4. Standard Error (SE): The possible range of the actual final score based upon the scaled T-score. For example, with a T-score of 52 and a SE of 2, the 95% confidence interval around the actual final score ranges from 48.1 to 55.9 ( $T\text{-score} \pm (1.96*SE) = 52 \pm (1.96*2) = 48.1 \text{ to } 55.9$ )

The final score is represented by the T-score, a standardized score with a mean of 50 and a standard deviation of 10 points.

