### **3.0 STUDY ENDPOINTS**

#### **3.1 Primary Endpoint**

The primary endpoint is caregiver HRQOL, as assessed by the PROMIS Global Health scale, at day 120 post-HCT. To be evaluable for caregiver HRQOL, the caregiver must complete this scale at day 120 post-HCT. Caregivers of patients who relapse or die before this endpoint will not be evaluable for this endpoint; both caregiver and patient will be censored on the date the patient was last examined. See **Appendix D** for a copy of all PROMIS PROs.

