### **5.10.2 General Analysis Guidelines**

Primary analyses for the primary, secondary, and exploratory endpoints will use the primary analysis population. Analyses of each endpoint in each population will follow the analysis plans, as described below. We expect minimal missing data ( $<5\%$ ) for the primary endpoint and secondary endpoints based on past experience with Roadmap 1.0 studies.

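### Section 5.7's 83 caregivers per arm leave about 65 evaluable on its own loss rates, not 67, and the allowance omits relapse, so the 0.80 power holds only if relapse adds little further loss

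*Combined protocol and SAP*

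**What the plan says.** Section 5.7 sets the target: "Our study will have power of 0.80". The test level is two-sided 0.05 and the standardised difference between arms is 0.5. The scale is taken to have a standard deviation of 10, so the effect is 5 points. The stated power is tied to a sample size: "if 67 caregivers are enrolled in each arm". Accrual is then raised to 83 per arm, "assuming a 5% failure to undergo BMT, 8% death before day 120, and 10% missing day 120 PRO from participants". The section describes these rates as inflated. The calculation was done by simulation in R, and the section does not name the test that was simulated.

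Four other places bear on the number who will be analysed:

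- Section 3.1: "Caregivers of patients who relapse or die before this endpoint will not be evaluable for this endpoint".
- Section 4.8: after a relapse, no further surveys are collected from the patient or the caregiver.
- Section 5.10.2: "We expect minimal missing data", put at under 5% for the primary endpoint.
- Section 5.11: the primary analysis is labelled intent-to-treat with every caregiver included. The test is a two-sample t-test, with the Wilcoxon rank sum test if the data look non-normal. Only the allogeneic stratum is powered.

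The synopsis gives 166 adult allogeneic dyads, 83 per arm, as a minimum.

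**The concern.** An attrition allowance should return the required number after the losses are taken. Here it does not, and it leaves out one class of loss that the protocol itself creates. Death and relapse both make a caregiver non-evaluable under section 3.1, but section 5.7 allows only for death. Autologous and pediatric dyads cannot make up the difference, because the powered comparison is confined to allogeneic dyads.

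If relapse removes a material share of caregivers, a null result in that one powered stratum would be read against a power the analysed sample did not have. The text also gives the reader two figures for missing questionnaires, 10% and under 5%, and two descriptions of who is analysed: all caregivers, or only those whose patient is alive and relapse-free at day 120.

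**Working it through.** **Inputs.** From section 5.7: two-sided alpha 0.05, power 0.80, difference 0.5 SD (5 points on an SD of 10), 67 required and 83 accrued per arm, losses of 5%, 8% and 10%. From section 5.4: equal allocation. From section 5.11: two-sample t-test. The relapse rate is not in the documents and is varied below.

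**Step 1, the plan's 67.** The exact (noncentral t) requirement for 0.80 power at an effect of 0.5 is 63.8, so 64 per arm. Power at 67 is 0.819. The stated 67 is therefore adequate for the t-test, with about three caregivers per arm to spare.

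**Step 2, the plan's 83.** The three rates sum to 23%, and 67 × 1.23 = 82.4, which rounds up to 83. This looks like the source of the figure, though the document does not say so. Multiplying by (1 + d) is not the inverse of losing a fraction d; the inflation should divide by (1 − d):

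- losses compounded: 0.95 × 0.92 × 0.90 = 0.7866, and 67 / 0.7866 = 85.2, so 86 per arm;
- losses added: 67 / 0.77 = 87.01, so 88 per arm.

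**Step 3, what 83 returns.**

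- compounded: 83 × 0.7866 = 65.3 per arm, t-test power 0.809;
- added: 83 × 0.77 = 63.9 per arm, t-test power 0.801.

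Both are short of 67, and both still meet 0.80.

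**Step 4, adding relapse.** Let r be the proportion lost to relapse and not already counted as death, missing questionnaire or failure to be transplanted. The evaluable number is 65.3 × (1 − r). Power reaches 0.80 at 63.77 per arm, so the break-even is r = 1 − 63.77/65.29 = 2.3%. With missing questionnaires at 5% (the upper limit in section 5.10.2), retention is 0.95 × 0.92 × 0.95 = 0.8303. That leaves 83 × 0.8303 = 68.9 per arm with power 0.83, and the break-even becomes 1 − 63.77/68.91 = 7.5%.

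| Assumed r | Evaluable per arm, 10% missing | t-test power | Evaluable per arm, 5% missing | t-test power |
|---|---|---|---|---|
| 0% | 65.3 | 0.81 | 68.9 | 0.83 |
| 5% | 62.0 | 0.79 | 65.5 | 0.81 |
| 10% | 58.8 | 0.77 | 62.0 | 0.79 |
| 20% | 52.2 | 0.72 | 55.1 | 0.74 |

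**The case against.** The strongest reply is that nothing has been lost. On the listed rates the t-test keeps 0.80 to 0.81, the rates are declared inflated, 166 allogeneic dyads is a floor, and relapse overlaps with death and missing questionnaires, so only part of it is an extra loss. All of that stands. It rules out the reading that the design fails to deliver 0.80 power: the 67-to-65 gap does not do so, and the effect of relapse depends on a rate the documents do not give. It does not dispose of the point, because the plan never assigns its slack to relapse or says how much relapse it can absorb.

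Three stronger readings are tempting and are not supported.

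- A reader might infer that 67 is a Wilcoxon requirement, since 63.8/0.955 = 66.8, and that 65 already fails for that test (power about 0.79). Section 5.7 names no test, section 5.11 puts the t-test first, and the 0.955 efficiency applies under normality, when the fallback would not be used.
- A reader might set the under 5% in section 5.10.2 against a total loss of about 21% (1 − 0.7866). That mixes missing questionnaires with deaths and untransplanted patients. The like-for-like comparison is 10% against under 5%, and an inflated planning rate can coexist with a lower expectation; the text should say so.
- A reader might say that sections 3.1 and 4.8 both treat relapse as they treat death. Only section 3.1 pairs the two; section 4.8 speaks of relapse alone.

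**Conclusion.** The point holds in conditional form. The inflation is wrong as arithmetic: 83 per arm yields about 65 evaluable caregivers (64 if losses are added), not 67. That error alone leaves t-test power at 0.80 to 0.81. The substantive gap is the missing relapse term. The margin is about 2.3% of non-overlapping relapse on the listed rates, or about 7.5% if 5% of questionnaires are missing. Beyond that, power falls to 0.77 at an assumed 10% and 0.72 at an assumed 20% on the listed rates.

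These figures assume an effect of 0.5 SD, exactly 83 allogeneic dyads per arm, losses that compound independently, and an analysis of evaluable caregivers only. The inconsistencies between sections 5.7 and 5.10.2, and between section 5.11 and sections 3.1 and 4.8, do not depend on the relapse rate. Overall this should be fixed, with its weight depending on that rate.

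**What to change.** In section 5.7, derive the allowance by dividing by (1 − d), and state that 83 per arm is expected to give about 65 evaluable allogeneic caregivers before relapse. Add a justified allowance for relapse not already counted as death or missing questionnaire, and give the resulting power. If the declared inflation of the rates or enrolment above 166 is meant to absorb relapse, say so and by how much.

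In section 5.10.2, reconcile the under 5% with the 10% in section 5.7 as rates of missing questionnaires, kept separate from deaths and untransplanted patients. Reconcile section 5.11's statement that every caregiver is included with the evaluability rule in sections 3.1 and 4.8, so that one analysis set is defined.

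These are text changes and need no extra patients. The downside is a slightly less favourable stated power. If the sponsor preferred to hold 67 evaluable per arm, the listed rates alone would need 86, and 10% additional relapse would need 67 / (0.7866 × 0.90) = 94.6, so 95; reporting the lower power honestly is the cheaper course.
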